### **3.2 Exclusion Criteria**

- Patient is pregnant or nursing

### **3.3 Informed Consent Process**

All participants will be provided a consent form describing the study with sufficient information for participants to make an informed decision regarding their participation. Participants must sign the IRB approved informed consent prior to participation in any study specific procedure. The participant must receive a copy of the signed and dated consent document. The original signed copy of the consent document must be retained in the medical record or research file.

### **3.4 Study Timeline**

#### **3.4.1 Primary Completion:**

The study will reach primary completion 36 months from the time the study opens to accrual. We estimate 75 patients will be enrolled.

#### **3.4.2. Study Completion:**

The study will reach study completion 36 months from the time the study opens to accrual.

## **4. IMAGING AGENT INFORMATION**

### **4.1 Study Agent/Device**

Digital PET/CT Scanner

### **4.2 Specify the source of the study agent/device.**

GE Healthcare

### **4.3 Describe how the agent will be requested and provide mailing address and phone number.**

Digital PET/CT Scanner present on Stanford Campus in the hospital.

### **4.4 Agent Accountability**

N/A

## **5. IMAGING SPECIFICS**

### **5.1 Modality or Modalities to be used**

Digital PET/CT

## **5.2 Details of Imaging (i.e. dynamic, static, number of scans, etc.)**

Patients will have  $^{99m}\text{Tc}$  MAA planar and SPECT/CT imaging as part of the standard SIRT planning protocol. These images are acquired after administration of 4 mCi of  $^{99m}\text{Tc}$  MAA in the Interventional Radiology suite. The patient will then be given  $^{90}\text{Y}$  Spheres (Glass or Resin), and after SIRT procedure, will be arrive to NM for digital PET/CT image acquisition with diagnostic contrast enhanced CT of the abdomen. We will be administering 50mL of iodinated contrast through IV during the CT scan. Next, PET images will be acquired in 3D mode using a single bed located over the liver, with a total acquisition time of approximately 30-minutes. The PET emission scan is corrected using the segmented attenuation data from the CT scan. The PET images are reconstructed both with a standard iterative algorithm (OSEM, two iterative steps, 28 subsets), as well as a regularized reconstruction algorithm provided by GE Healthcare. All images are reformatted into axial, coronal, and sagittal views and viewed with the software available in the Nuclear Medicine and Molecular Imaging Clinic (MIM Software, Cleveland, OH).

## **5.3 Details of processing/analysis**

The  $^{99m}\text{Tc}$  MAA planar and SPECT/CT imaging and the PET/CT scans will be interpreted by ABNM certified Nuclear Medicine physicians. All investigators have significant clinical experience and will be blinded to the participant's medical history and the results of other imaging modalities. A consensus read will be obtained for each scan to assess image quality. Each lesion will be tabulated and a comparison of lesion detection and radiation absorbed dose by each scanner will be conducted.

Currently,  $^{99m}\text{Tc}$  MAA planar and SPECT/CT images only simulate  $^{90}\text{Y}$  radiopharmaceutical biodistribution within the liver and tumor(s). Incorporating SurePlan software (MIM) to analyze the PET/CT images will determine final dose-volume histogram (DVH) within the liver and tumor (s) post  $^{90}\text{Y}$  injection. Additionally,  $^{90}\text{Y}$  PET/CT and  $^{99m}\text{Tc}$  MAA planar and SPECT/CT biodistribution images can be compared to evaluate  $^{99m}\text{Tc}$  MAA simulation accuracy. Results of this image comparison could potentially impact clinical decision-making moving forward. This information will be reported and shared with the referring physicians involved in the care of the patient.

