### 1.2 Secondary Objective

- To determine the superior accuracy in both distribution and dosimetry of  $^{90}\text{Y}$  PET/CT post SIRT imaging compared to  $^{99\text{m}}\text{Tc}$  MAA planar and SPECT/CT imaging

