## **2.5 Study Design**

This is a non-randomized prospective trial. Patients who are referred to Nuclear Medicine and Interventional Radiology for  $^{99\text{m}}\text{Tc}$  MAA SPECT/CT followed by SIRT will be asked to have imaging done using the digital PET/CT scanner following the  $^{90}\text{Y}$  SIRT injection. This could be done during their mandatory 2-hr rest while lying flat (due to closure device), after their 2-hr rest period, or the next day after the participant's SIRT procedure. We will administer 50mL of IsoVue 370 contrast to the participant during the CT scan, if there are no contraindications. We will not inject additional radiopharmaceutical; instead, we will use the already administered  $^{90}\text{Y}$  from SIRT. This is possible because the digital PET/CT has very sensitive PET detectors. A very small amount of radiation (5 mSv) will be given by the attenuation correction CT scan in the second PET/CT.

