## **10.5 Secondary outcome measure**

We will assess the radiopharmaceutical distribution and dosimetry accuracy of  $^{90}\text{Y}$  PET/CT by comparing visual distribution discrepancies (if any) and numerical values calculated by SurePlan from both  $^{99m}\text{Tc}$  MAA SPECT/CT and  $^{90}\text{Y}$  PET/CT images.

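### The per-scanner lesion-detection comparison in section 5.3 mixes particle delivery with scanner performance and gives no rule for tumours seen on one scan only

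*Combined protocol and SAP*

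**What the plan says.** All references are to the combined protocol and SAP.

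- **Section 5.3**, first paragraph: "Each lesion will be tabulated and a comparison of lesion detection and radiation absorbed dose by each scanner will be conducted". No section defines detection, names a reference list of lesions, or says how a lesion seen on one scan only is classified.
- **Section 5.3**, second paragraph: 99mTc "MAA planar and SPECT/CT images only simulate" the 90Y distribution. It adds that 90Y PET/CT and MAA "biodistribution images can be compared to evaluate" how accurate the MAA simulation was.
- **Section 2.5**, on the PET: "We will not inject additional radiopharmaceutical; instead, we will use the already administered" 90Y.
- **Section 1.2** sets the secondary objective: "To determine the superior accuracy in both distribution and dosimetry of" 90Y PET/CT relative to MAA imaging.
- **Section 10.5** assesses the distribution and dosimetry accuracy of 90Y PET/CT by "comparing visual distribution discrepancies (if any) and numerical values calculated by SurePlan from both" scans.
- **Section 5.2** pairs the PET with a diagnostic contrast-enhanced CT of the abdomen. Sections 2.5 and 8.1 allow the contrast to be omitted.
- **Section 11.5** plans no statistical analysis.

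**The concern.** A comparison of detection between two scanners presumes that both look for the same thing, and that a lesion shown by one and not the other tells us about the instruments. Here the two emission images come from two separate administrations of particles. A tumour can lack uptake because no particles arrived or because the scanner failed to show particles that did arrive, and a count per scanner cannot tell these apart.

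The same image pairs also feed the distribution comparison, where a one-scan-only tumour is a discrepancy between simulation and treatment. The plan does not say which scan a discrepancy counts against. A report that PET detected more, or fewer, lesions than MAA SPECT/CT would invite a conclusion about the scanner that the data cannot support. It could also appear beside a distribution result that points the other way on the same tumours. Section 5.3 says the image comparison could influence clinical decisions and that the information will be shared with referring physicians, so the wording of the result matters.

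**Working it through.** The documents give no figure for lesion counts, detection or discordance, so there is nothing to reproduce on this point. The only related number is the accrual of 75 patients (25 per year × 36/12 years = 75), and the argument does not depend on it.

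**Step 1. What each emission image shows.** By 5.3, MAA is a simulation of where 90Y will go. By 2.5, the PET images the 90Y already given. Uptake in a tumour therefore requires delivery to that tumour and a scanner able to show it. This holds for the emission images only; the CT component can show a tumour without uptake.

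**Step 2. Which scan is judged.** Section 5.3 first compares detection between scanners and then compares the images to judge MAA. Section 10.5 compares the images to judge 90Y PET/CT. Section 1.2 takes PET to be the more accurate scan. No section says which scan a disagreement counts against.

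**Step 3. Effect on a tally.** Let *a* = tumours with uptake on both scans, *b* = MAA only, *c* = 90Y PET only, *d* = neither, and *n* = *a* + *b* + *c* + *d*.

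- PET detection = (*a* + *c*)/*n*
- MAA detection = (*a* + *b*)/*n*
- PET minus MAA = (*c* − *b*)/*n*
- Share of MAA-positive tumours confirmed on PET, if PET were the reference = *a*/(*a* + *b*)

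With assumed counts (*n* = 100, *c* = 5, *d* = 5, so *a* = 90 − *b*):

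| *b* (MAA only) | PET detection | MAA detection | PET minus MAA | MAA-positive confirmed on PET |
|---|---|---|---|---|
| 0 | 95% | 90% | +5 points | 90/90 = 100% |
| 5 | 90% | 90% | 0 points | 85/90 = 94.4% |
| 10 | 85% | 90% | −5 points | 80/90 = 88.9% |
| 20 | 75% | 90% | −15 points | 70/90 = 77.8% |

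As *b* grows, the detection columns move against PET. If PET were the reference, the last column would move against MAA. The same cell drives both.

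**Step 4. Why the tally cannot be decomposed.** Write *b* = *b*1 + *b*2, where *b*1 tumours received no 90Y and *b*2 received 90Y that the PET did not show. Only the sum is observed. Take *b* = 10, so that 80 + 5 = 85 tumours are positive on PET. Assume that all 85 truly received 90Y and that the 5 tumours seen on neither scan did not.

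- All ten undelivered (*b*1 = 10): PET missed 0 of 85 tumours that received 90Y, or 0%.
- All ten delivered but not shown (*b*2 = 10): PET missed 10 of 85 + 10 = 95, or 10.5%.

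The tally is 85% against 90% in both cases. It is compatible with any PET miss rate from 0% to 10.5% under these assumed counts.

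**The case against.** The strongest reply is that the protocol contains no scoring rule. Section 5.3 says only that lesions are tabulated and detection compared. It mentions no miss, score or ranking, and the MAA-accuracy comparison is worded as something that can be done. Visibility on each scan and agreement between scans are also different questions, whose answers may differ without contradiction. Lesion detection is not a stated objective or outcome: the primary outcome is image quality on a Likert scale, the secondary concerns distribution and dosimetry, and no test depends on the count.

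Most of this stands, and it rules out several stronger readings that a reader might infer:

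- *The plan scores one lesion in opposite directions.* It does not. It leaves both readings open and chooses neither.
- *A tumour positive on MAA and negative on PET is a correct PET result.* The documents do not support this. Section 2.1 describes 90Y PET as imaging low-abundance pair production, with suboptimal quality on scanners then available, so delivered 90Y could go unseen.
- *A tumour is visible only if particles reached it.* The contrast-enhanced CT in 5.2 can show a tumour without uptake. Whether detection may use the CT is not stated, which adds to the ambiguity.
- *The count says nothing about the scanner.* That is too strong. Scanner performance contributes to it but cannot be separated from delivery.
- *False foci on PET would reverse the ranking.* The documents give no false-focus rate for either scan, and nothing justifies assuming such foci on PET alone.

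What survives the reply is that a per-scanner comparison is planned, its result is not interpretable as scanner performance, and one-scan-only tumours have no rule. The reason given in 11.5 for omitting statistical analysis, that the two modalities differ inherently, makes an unqualified detection count harder to defend.

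**Conclusion.** The point holds in limited form. The detection comparison in 5.3 cannot be read as scanner performance, because uptake on each scan depends on delivery as well as on the instrument. A tumour with uptake on MAA only could be an MAA prediction failure or a PET sensitivity failure, and the plan does not say how it is to be read.

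The size of the effect cannot be estimated from the documents. The figures in the working rest on assumed counts and show that the direction of the tally depends on the one-scan-only cells, not how often this would happen. The primary image-quality comparison is not in question here. The correction is still worthwhile, because the comparison is stated in the plan, would mislead if reported as it stands, and is cheap to replace.

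**What to change.** In 5.3, replace the per-scanner detection comparison with a paired four-cell table of tumours: uptake on both scans, MAA only, 90Y only, neither. Report it under 10.5 as concordance of distribution, crediting neither scanner with a detection and treating neither as truth. State the following with it:

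- **Tumour list.** Take it from pre-treatment diagnostic imaging already in the record, independent of both study scans. The documents name no such list, so its availability for every patient is an assumption to confirm. The eligibility checklist in the appendix does accept radiology results and record review as supporting documents.
- **Timing.** Match the list to the reads only after the blinded reads are locked, because 5.3 and 10.4 blind the readers to history, diagnosis and the other scan.
- **Role of CT.** Classify uptake on the emission images, and report tumours visible on CT alone separately.
- **Unmatched foci.** List foci that match no listed tumour separately for each scan, outside the four cells.

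The cost is a wording change in 5.3 and 10.5, one table, and a small unblinded matching step after the reads. Image acquisition and the blinded reading sequence are unchanged. The trial gives up a headline lesion-detection count.

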## **6. STUDY PROCEDURES**

### **6.1 Criteria for Removal from Study**

The Protocol Director may withdraw subjects from the study for one or more of the following reasons: failure to follow the instructions of the Protocol Director and/or study staff; determination that continuing the participation could be harmful to the subject; the study is cancelled or other administrative reasons.

### **6.2 Alternatives**

The alternative is to not participate in the study.

## 7. STUDY CALENDAR

	Pre-Study	Day 1-2	1 Months
Informed consent	X		
Demographics	X		
Medical history	X		
99m Tc MAA planar and SPECT/CT imaging	X		
SIRT followed by digital PET/CT		X	
Data analysis			X

## 8. ADVERSE EVENTS AND REPORTING PROCEDURES

### 8.1 Potential Adverse Events

We will not inject additional radiopharmaceutical; instead, we will use the already administered Y from SIRT. This is possible because the digital PET/CT has very sensitive PET detectors. There will be additional radiation from the contrast-enhanced CT used in the research scan. This research study involves exposure to radiation from CT scans that is not necessary for participant's medical care and is for research purposes only. The additional amount of radiation exposure is up to about 5.0 mSv, which is approximately equal to 10% of the limit that radiation workers (for example, a hospital x-ray technician) are allowed to receive in one year. This amount of radiation involves minimal risk and is necessary to obtain the research information desired.

There is a small volume (50 ml) of iodinated contrast to be given during the CT scan. This will require the introduction of an intravenous (IV) catheter. As with any IV catheter, there is some discomfort associated with introduction of the catheter. There can also be some redness and swelling associated with the catheter placement, but these will usually subside quickly. With the contrast injection, there is a risk of contrast extravasation (leakage) into the skin which can cause swelling and mild pain. You will be offered a hot or cold compress to help mobilize any extravasated contrast, and if very severe, you would be offered the appropriate supportive care, which in rare instances includes transfer to the emergency room and surgical consultation.

If there is any reason for you not to have the iodinated contrast, it will be omitted at physician discretion.

## **8.2 Adverse Event Reporting**

We do not anticipate hazardous situations for the subjects as a result of this protocol. However, procedures will be in place for verification of correct radiopharmaceutical dose and route of administration (i.e., each dose will be double checked for dosimetry and quality by a researcher and technologist). Adverse events will be graded according to CTCAE v4.0. Both Serious and Non-Serious Adverse Events will be clearly noted in source documentation and listed on study specific Case Report Forms (CRFs). The Protocol Director (PD) or designee will assess each Adverse Event (AE) to determine whether it is unexpected according to the Informed Consent, Protocol Document, or Investigator's Brochures, and related to the investigation. For the purposes of this study, the reporting period ends at scan completion. There will be no follow-up procedures for this study. Adverse events will be reported in adherence to Stanford University's internal Adverse Event SOP.

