# **3. PARTICIPANT SELECTION AND ENROLLMENT PROCEDURES**

## **3.1 Inclusion Criteria**

- Patient is  $\geq$  18 years old at the time of the scan
- Patient provides written informed consent
- Patient is referred for  $^{90}\text{Y}$  SIRT radioembolization of liver tumor(s)
- Patient is capable of complying with study procedures

- Patient is able to remain still for duration of imaging procedure (approximately 30 minutes total for digital PET/CT)

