### **9.3 Data and Safety Monitoring**

During the clinical investigation, the Protocol Director will evaluate the progress of the trial, including periodic assessments of data quality and timeliness, participant recruitment, accrual and retention, participant risk versus benefit, performance of trial sites, and other factors that can affect study outcome. Monitoring of the trial will occur every 12 weeks and a record of monitoring activities will be maintained by the study team.

The Stanford Cancer Institute Data and Safety Monitoring Committee (DSMC) will audit study related activities to determine whether the study has been conducted in accordance with the protocol, local standard operating procedures, FDA regulations, and Good Clinical Practice (GCP). This may include review of regulatory binders, case report forms, eligibility checklists, and source documents. In addition, the DSMC will regularly review serious adverse events and protocol deviations associated with the research to ensure the protection of human subjects. Results of DSMC audits will be communicated to the IRB and the appropriate regulatory authorities at the time of continuing review, or in an expedited fashion, as needed.

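### Adverse event reporting ends at scan completion, about 30 minutes after the research contrast injection, so the later course of contrast- or catheter-related events has no planned collection

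*Combined protocol and SAP*

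**What the plan says.** Section 8.2 (Adverse Event Reporting) asks for events to be graded by CTCAE v4.0, entered in source documents and case report forms whether serious or not, and assessed for expectedness and relatedness. It then closes collection: "For the purposes of this study, the reporting period ends at scan completion". The next sentence reads: "There will be no follow-up procedures for this study". The section also defers to an institutional adverse event procedure whose content is not reproduced.

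Section 5.2 gives the order of the imaging. Contrast comes with the CT: "We will be administering 50mL of iodinated contrast through IV during the CT scan". The PET acquisition follows, "with a total acquisition time of approximately 30-minutes".

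Section 8.1 places the contrast-enhanced CT within the study: "There will be additional radiation from the contrast-enhanced CT used in the research scan". It names discomfort, redness and swelling from the catheter, and contrast extravasation with swelling and mild pain. For a very severe extravasation it describes supportive care, "which in rare instances includes transfer to the emergency room and surgical consultation". It also allows contrast to be left out at the physician's discretion.

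Section 9.3 says that "the DSMC will regularly review serious adverse events and protocol deviations associated with the research". The calendar in section 7 has no adverse event row and no participant contact after Day 1-2. Its 1-month column holds data analysis only.

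**The concern.** Section 2.5 says that no radiopharmaceutical is added for the study. The contrast, and the catheter it needs, are therefore what the study itself introduces into the patient. That the contrast is research-only is a close inference: 8.1 says so explicitly of the CT radiation and describes the contrast-enhanced CT as part of the research scan.

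For that exposure, 8.1 describes a severe course involving an emergency room and a surgical opinion, while 8.2 stops collecting when the scanner stops. An extravasation noted as mild at the scan could worsen afterwards, and nothing in the visible text says that its grade, its seriousness or its outcome would be updated. A contrast- or catheter-related event that first comes to notice after the scan has no planned record at all. The data safety committee can review only what has been collected, and a statement that no such events occurred would describe only the period up to the end of the scan.

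**Working it through.** This is a comparison of sections with one piece of timing. No sample size, error rate or effect size bears on it.

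**Inputs**

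- End of reporting: completion of the scan (section 8.2).
- Follow-up after that: none (section 8.2).
- Contrast: 50 mL, given during the CT (section 5.2).
- PET: about 30 minutes, acquired after the CT (section 5.2).
- Imaging time in the eligibility criteria: "approximately 30 minutes total for digital PET/CT" (section 3.1).
- Participants: 75 expected (sections 3.4.1 and 11.3), not all of whom need receive contrast (sections 2.5 and 8.1).

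**Time from contrast to the end of reporting**

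Window = CT time remaining after the injection + any changeover + PET time.

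- If the 30 minutes is PET alone (5.2), the window is about 30 minutes plus whatever remains of the CT.
- If the 30 minutes is the whole PET/CT (3.1), the window is 30 minutes less the CT time up to the injection, so slightly under 30 minutes.

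Both readings give about 30 minutes. Section 2.5 allows the scan during the rest period after SIRT, after it, or on the next day. That choice does not change the window, because the window is tied to the scan.

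**What the window covers, item by item**

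| Item | Collection in the visible text |
|---|---|
| Catheter discomfort, redness, swelling: onset at placement | Inside the window; can be recorded |
| Extravasation: onset at injection | Inside the window; can be recorded |
| Worsening of either after the scan | None planned |
| Final CTCAE grade, seriousness and outcome, if settled after the scan | None planned |
| Contrast- or catheter-related event first noticed after the scan | None planned |

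**Is there another route?**

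- The section 7 calendar offers no contact after Day 1-2.
- Section 9.3 provides for review of serious events but states no collection period of its own.
- The institutional procedure cited in 8.2 might provide one, but this cannot be checked from the documents. A study-specific end point standing beside an institutional procedure also leaves staff unsure which governs.

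**The case against.** The strongest reply is that the listed harms all begin inside the window. Catheter effects start at placement and extravasation starts at injection, both before the PET. The emergency room and the surgical opinion are management of an extravasation, not separate adverse events, and 8.2 does not say that an event already recorded must be closed or left ungraded. A very severe extravasation might itself end the scan. Serious events with onset in the window still reach the committee. No objective or outcome measure concerns contrast safety.

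Most of this stands, and it rules out several stronger readings that a reader might be tempted to draw:

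- **That 8.1 lists harms as lasting beyond the scan.** It gives no durations, names no late-onset reaction, and describes the catheter effects as usually short-lived. The later course is an inference from the emergency room and surgery wording.
- **That the listed harms cannot be recorded, or that the severe ones are ruled out of reporting.** Their onset can be recorded.
- **That the committee will be deprived of serious events.** Only information arising after the scan is in question, and the institutional procedure may require it.
- **That an upper confidence limit should be put on the event rate if none is seen.** The plan does not set out to estimate a contrast event rate, and the number exposed may be below 75.

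What the reply does not supply is a provision for following an event after the scan. The visible text gives an end point and says there is no follow-up. That an open event is not expressly closed does not create a plan to re-grade it or to record how it ended.

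**Conclusion.** The concern holds in a limited form. Followed as written, 8.2 ends collection about 30 minutes after a contrast injection that belongs to the research scan. Two things then have no planned collection in the visible text: the later worsening, final grade, seriousness and outcome of a contrast- or catheter-related event that began during the scan, and any such event first noticed afterwards.

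The reach is up to 75 participants, reduced by those in whom contrast is omitted. The documents give no event rate, so the number of affected records cannot be stated; 8.1 calls the severe course rare. The image-quality and dosimetry comparisons are not touched. What is affected is the completeness of safety reporting.

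The conclusion rests on three assumptions: that the contrast is given for research, that the severe course in 8.1 would usually extend past the scan, and that the unseen institutional procedure does not already fill the gap. If it does fill the gap, the remaining need is to say so in 8.2. The change is worth making because it is cheap and specific, but it is not a fault that undermines the study.

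**What to change.** Amend 8.2 so that it agrees with 8.1:

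1. Follow any contrast- or catheter-related event to resolution, recording its final grade, seriousness and outcome.
2. Make such events reportable when first noticed after the scan, for a period that the investigators set and state.
3. Ascertain them by a medical-record check timed with the 1-month data-analysis step, and add a matching row to the section 7 calendar.
4. Attribute each event to contrast or catheter, or to SIRT. Section 8.2 already requires a relatedness assessment, so this makes an existing step more specific.
5. State how this rule relates to the institutional procedure and which governs if they differ.

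This changes what is recorded, not how patients are managed. The cost is a short amendment and one record check per participant. The check is a small new task, since the 1-month step is at present for image analysis and not for safety. Section 2.1 describes pain, nausea, vomiting and fatigue after radioembolization, so some post-SIRT events will surface in the check and need attribution. Limiting the rule to contrast- and catheter-related events keeps that burden down.
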